### 7.1.3.5 Benefit/Risk Assessment

Fipaxalparant (HZN-825) is a new therapeutic agent under development for treating fibrotic diseases, including SSc. The anti-inflammatory and anti-fibrotic properties of LPAR1 antagonism have been demonstrated in both animal models and in a Phase 2 clinical trial. Positive changes in mRSS, HAQ-DI and LPAR1 pathway genes were detected in the completed Phase 2a trial in diffuse cutaneous SSc. Results of trials to date support the safety and potential efficacy of 300 mg BID for up to 24 weeks of treatment. The exposure, PK and safety profiles of fipaxalparant (HZN-825) were similar across the completed trials.

Based on the cumulative safety data available to date on fipaxalparant (HZN-825), transaminase increase has been evaluated as an important identified risk and [REDACTED], drug-drug interactions, and embryo-fetal toxicity are considered as important potential risks. No severe AEs or SAEs were reported in healthy subjects in Phase 1 trials. TEAEs of [REDACTED] [REDACTED], postural dizziness, flatulence and abdominal pain were slightly more frequent in fipaxalparant (HZN-825)-treated than in placebo-treated subjects. [REDACTED] was mainly observed in healthy subjects and tended to be less marked in subjects with diffuse cutaneous SSc treated with fipaxalparant (HZN-825). The potential safety risk of fipaxalparant

(HZN-825) due to drug-drug interactions is considered low as medications that may have potential interactions with fipaxalparant (HZN-825) are restricted in this protocol (Section 9.4.9).

AESIs are considered monitorable. Taking into account mitigation measures to minimize risk to subjects in this trial, the potential risk identified in association with fipaxalparant (HZN-825) treatment and the trial as a whole are justified by the anticipated benefits that may be afforded to subjects.

More detailed information on the benefits and risks of fipaxalparant (HZN-825) is provided in the Investigator's Brochure Section 6.2 and Section 12.

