#### **9.3.3.1 Removal of Subjects from Treatment**

The primary reason for discontinuation from trial drug should be recorded on the eCRF using one of the following categories:

- AE or clinically significant laboratory/electrocardiogram (ECG) abnormality. The subject experiences an AE or clinically significant laboratory/ECG abnormality that imposes an unacceptable risk to the subject's health, or the subject is unwilling to continue receiving treatment because of an AE or clinically significant laboratory/ECG abnormality. Subjects who discontinue trial drug due to an AE or clinically significant laboratory/ECG abnormality will remain in the trial unless they withdraw from the trial for another reason. In such cases, if the situation is not an immediate emergency, the Investigator should contact the trial Medical Monitor.
- Drug-induced liver injury. Trial drug discontinuation should be considered if:
  - alanine aminotransferase (ALT) or aspartate aminotransferase (AST)  $>8 \times$  upper limit of normal (ULN)
  - ALT or AST  $>5 \times$  ULN for more than 2 weeks

- ALT or AST  $>3 \times$  ULN and (total bilirubin [TBL]  $>2 \times$  ULN or international normalized ratio  $>1.5$ )
- ALT or AST  $>3 \times$  ULN with the appearance of fatigue, nausea, vomiting, right upper quadrant pain or tenderness, fever, rash and/or eosinophilia ( $>5\%$ )

Subjects who have ALT or AST levels  $>3 \times$  ULN confirmed in a repeat test need to undergo close observation as prescribed by the [FDA guidance](#) on drug-induced liver injury (refer to Appendix 17.15). Close observation includes repeating liver enzyme and serum bilirubin tests 2 or 3 times weekly. Frequency of retesting can decrease to once a week or less if abnormalities stabilize and the subject is asymptomatic. The decision to rechallenge the subject is to be discussed and agreed upon by the Investigator, and Amgen Medical Monitor.

- Lack of efficacy. Discontinuation of trial drug due to lack of efficacy is at the discretion of the Investigator or subject and may occur if the Investigator determines that trial drug administration is not benefitting the subject. Subjects who discontinue trial drug due to lack of efficacy will remain in the trial for scheduled safety and efficacy assessments through Week 52 unless they also withdraw from the trial for another reason.

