#### **10.3.3.2 Summaries Liver Function Tests**

Liver-related abnormalities after initial trial drug dosing will be examined and summarized by treatment group using the number and percentage of subjects who were reported to have the following laboratory test values for postbaseline measurements:

- Aspartate aminotransferase (AST):
  - (a) > 3 times of the upper limit of reference range (ULN);
  - (b) > 5 x ULN
  - (c) > 8 x ULN;
  - (d) > 20 x ULN
- Alanine aminotransferase (ALT):
  - (a) > 3 x ULN;
  - (b) > 5 x ULN
  - (d) > 8 x ULN;
  - (e) > 20 x ULN
- AST or ALT:
  - (a) > 3 x ULN;

- (b)  $> 5 \times \text{ULN}$
- Total bilirubin:
  - (a)  $> 1.5 \times \text{ULN}$ ;
  - (b)  $> 2 \times \text{ULN}$
  - (c)  $> 3 \times \text{ULN}$
- Alkaline phosphatase (ALP):
  - (a)  $> 1.5 \times \text{ULN}$ ;
  - (b)  $> 2 \times \text{ULN}$
  - (c)  $> 3 \times \text{ULN}$
- Gamma Glutamyl Transferase (GGT):
  - (a)  $> 2.5 \times \text{ULN}$ ;
  - (b)  $> 5 \times \text{ULN}$
  - (c)  $> 20 \times \text{ULN}$
- Potential Hy's Law: AST or ALT  $> 3 \times \text{ULN}$  and total bilirubin  $> 2 \times \text{ULN}$

The summary will include data from all postbaseline visits up to 28 days after the last dose of trial drug.

For individual laboratory tests, subjects will be counted once based on the most severe postbaseline values. For both the composite endpoint of AST or ALT and total bilirubin, subjects will be counted once when the criteria are met at the same postbaseline visit date. The denominator is the number of subjects in the Safety Analysis Set who have non-missing postbaseline values of all relevant tests at the same postbaseline visit date.

A listing of subjects who met at least 1 of the above criteria will be provided.

Evaluation of Drug-Induced Serious Hepatotoxicity (eDISH) plots will be produced.

Liver function data will be evaluated from Trail and HZN-825 Baselines to the end of HZNP-HZN-825-302 separately as needed.

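### The same-date rule leaves a subject out of the potential Hy's Law row if ALT and AST are back to 3 x ULN or less whenever bilirubin exceeds 2 x ULN; add a windowed row

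*SAP*

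**What the plan says.** SAP 10.3.3.2 lists liver abnormalities to be tabulated by treatment group. The last is headed "Potential Hy's Law: AST or ALT" above 3 x ULN, combined with total bilirubin above 2 x ULN. Three rules govern the counts:

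- Single tests: "For individual laboratory tests, subjects will be counted once based on the most severe postbaseline values". There is no timing condition.
- The transaminase and bilirubin composite: "subjects will be counted once when the criteria are met at the same postbaseline visit date".
- Denominator: Safety Analysis Set subjects with "non-missing postbaseline values of all relevant tests at the same postbaseline visit date".

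On data scope, "The summary will include data from all postbaseline visits up to 28 days after the last dose of trial drug". The section also promises a listing of subjects who meet any one of the criteria, and "Evaluation of Drug-Induced Serious Hepatotoxicity (eDISH) plots will be produced". It does not say whether the plot pairs each subject's peaks or values from one date.

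In the protocol, section 7.1.3.5 says that "transaminase increase has been evaluated as an important identified risk". Under section 9.3.3.1, "Close observation includes repeating liver enzyme and serum bilirubin tests 2 or 3 times weekly" once a transaminase above 3 x ULN is confirmed. Appendix 17.15 asks for a repeat of enzymes and bilirubin within 48 to 72 hours. It allows that repeat to be run locally, with the results entered in the case report form.

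**The concern.** Transaminase and bilirubin need not exceed their limits on the same day. If transaminases peak and fall to 3 x ULN or less before bilirubin first exceeds 2 x ULN, no single date satisfies both conditions. The subject then scores zero in the row that readers turn to for serious hepatotoxicity. The protocol's serial retesting puts several dated results inside one episode, so such a sequence can be seen in the data, yet the summary has no row for it.

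At stake is the completeness of one descriptive safety row, in a 52-week extension of a drug with a named transaminase risk.

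**Working it through.** The documents give no expected rate or sample size for this row, so there is no planned figure to reproduce. The check is whether the rule can miss an episode, and under what condition.

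**1. Condition for a miss.** Same-date rule: count the subject if some date d has max(ALT, AST)(d) > 3 and TBL(d) > 2, in multiples of ULN. A subject who exceeds both limits at some time is missed exactly when ALT and AST are both ≤ 3, or unmeasured, on every date with TBL > 2. A bilirubin rise after the ALT peak is not enough for a miss.

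**2. Direction.** Windowed rule: count if some date d has max(ALT, AST)(d) > 3 and some date d2 has TBL(d2) > 2, with 0 ≤ d2 − d ≤ w. Setting d2 = d recovers the same-date rule. The same-date count is therefore never larger than the windowed count.

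**3. Invented episodes.** These are not trial data. AST is assumed no higher than ALT. Entries are day: ALT / TBL.

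| Subject | Course | Same date | Windows of 7, 14, 30 days |
|---|---|---|---|
| A | 0: 8 / 1; 3: 6 / 1.6; 7: 4 / 2.5 | counted | counted in all |
| B | 0: 5 / 1; 3: 3.8 / 1.6; 7: 2.5 / 2.5 | missed | counted in all |
| C | 0: 5 / 2.5 | counted | counted in all |
| D | 112: 5 / 1; 280: 1 / 2.5 | not counted | not counted in any |
| E | 100: 6 / 1.6; 103: 3.4 / 1.9; 106: 2.8 / 2.4 | missed | counted in all |

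Subject E follows the protocol's retest spacing. The first crossings are 106 − 100 = 6 days apart. The last ALT above 3 is on day 103, so a window of 106 − 103 = 3 days already captures the case. Subject D, with crossings 280 − 112 = 168 days apart, shows why a window is preferable to pairing peaks from any time.

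**4. How long ALT stays above 3 x ULN.** Assume a log-linear fall from peak P (x ULN) with half-life h, so days = h × log2(P/3). The half-lives are assumptions and are not in the documents.

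| Peak | h = 2 days | h = 4 days | h = 7 days |
|---|---|---|---|
| 4 | 0.8 | 1.7 | 2.9 |
| 5 | 1.5 | 2.9 | 5.2 |
| 8 | 2.8 | 5.7 | 9.9 |
| 20 | 5.5 | 10.9 | 19.2 |

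A bilirubin rise a few days after the peak may be caught or missed. Misses are likelier after modest or fast-falling peaks.

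**5. Scale of one miss.** For assumed totals of 250 and 100 treated subjects, 1/250 = 0.4% and 1/100 = 1.0%, against 0% reported. This shows what one subject weighs. It does not estimate how often a miss occurs.

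**The case against.** The same-date rule is explicit and prespecified, and the laboratory summaries are descriptive with no formal testing. Protocol 9.3.3.1, which pairs a transaminase above 3 x ULN with bilirubin above 2 x ULN (or INR above 1.5), says nothing about timing, so the SAP does not contradict it. No window length has a source in the documents. A missed subject is also not hidden: the worst-value rows count both crossings, the liver listing names the subject, and a chronological laboratory listing (SAP 10.3.3.1) shows the course. All of this stands, and it limits the point to one row.

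It does not remove the point. The listing takes in anyone who meets any single criterion, including alkaline phosphatase or GGT alone, so it gives no count of sequential cases. The eDISH plot cannot be relied on to show them while its pairing rule is unstated.

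A reader might infer more than the documents support:

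- *That the subject is not counted at all for the identified liver risk.* That risk is transaminase increase, which is counted on worst values with no date condition.
- *That frequent retesting makes a miss more likely.* Retests measure enzymes and bilirubin together and one qualifying date is enough, so extra paired draws can only add chances to qualify.
- *That the plot will contradict the table because it uses peak values.* The SAP does not say which values it plots.

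**Conclusion.** The point holds in a limited form. The potential Hy's Law row omits any subject whose ALT and AST are both at or below 3 x ULN, or unmeasured, on every date with bilirubin above 2 x ULN. Relative to a windowed count, the error runs only downward. It affects this row alone.

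Its frequency in this trial cannot be derived from the documents; the episodes, half-lives and subject totals used in the check are assumptions. It might be tempting to conclude that one missed case would overturn the liver-safety conclusion. The documents set no decision rule on this row, so that does not follow. This is a cheap improvement to the summary, not a defect that undermines the liver assessment.

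**What to change.** In SAP 10.3.3.2:

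1. Keep the same-date row and add a supplementary row: total bilirubin above 2 x ULN on the same date as, or within a prespecified window after, ALT or AST above 3 x ULN. Thirty days is one example; the length is for the sponsor to choose before database lock.
2. State that scheduled, unscheduled and local retest results all count. SAP 7.4 picks one value per visit, and the SAP is silent on the local repeats that Appendix 17.15 allows.
3. Give the new row a denominator that does not require the tests to fall on one date.
4. State how the eDISH plot pairs transaminase and bilirubin values.
5. In the liver listing, flag subjects who meet the windowed rule and show the dates of both crossings.

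The cost is one table row and a few lines of programming, with no change to patient care. The downside is that a window may pick up an unrelated bilirubin rise, which the dated listing lets reviewers assess.

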#### **10.3.4 Vital Sign**

Vital signs (blood pressure, heart rate, respiratory rate, temperature) will be measured at all clinic visits.

Descriptive summaries of observed and change from baseline values will be presented for each vital sign parameter and weight by treatment group and visit. A shift table for vital signs by RCTC grade and visit will be summarized.

In the case of multiple values in an analysis window, data will be selected for analysis as described in the TLF shells document. No formal statistical testing is planned.

A by-subject listing of vital signs and weight will be provided by subject ID number and time point in chronological order. High or low values will be flagged.

All data will be evaluated from Trail and HZN-825 Baselines to the end of HZNP-HZN-825-302 separately as needed.

### 10.3.5 Electrocardiogram Results

12-lead Electrocardiogram (ECG) will be performed at Screening (Baseline) and Weeks 1, 4, 16, 28, and 52. The results will be recorded as normal or abnormal on the eCRF and all abnormal results will be evaluated as clinically significant (CS) or not clinically significant (NCS) by the investigator.

Descriptive summaries of observed and change from both baselines values will be presented for each ECG parameter by treatment group and visit, including HR, PR, QRS, QT, and QTcF. ECG shift tables will be presented providing the count of subjects with each type of finding (normal, abnormal – NCS, or abnormal – CS) at both baselines compared to each post-baseline visit by treatment group with percentages based on subjects in the Safety Analysis Set with a non-missing value at the baseline and post-baseline visit.

Further, a summary will be provided for the count and percentage by classified categories. The abnormal post-dose QTcF interval values obtained during the trial will be summarized within the following categories:

- > 450 msec
- > 480 msec
- > 500 msec
- QTcF increase from Baseline > 30 msec
- QTcF increase from Baseline > 60 msec

Percentages will be based on the number of subjects in the Safety Analysis Set with at least one post-baseline value. Similar summaries will be provided by visit with the denominator based on the number of subjects with data at the given visit.

All ECG data will be evaluated from Trail and HZN-825 Baselines to the end of HZNP-HZN-825-302 separately as needed.

## 11 Pharmacokinetic Analyses

PK data will be analyzed using the PK Analysis Set. Plasma concentrations of HZN-825 and metabolite(s) (if applicable) in HZNP-HZN-825-302 will be summarized descriptively, including arithmetic means, standard deviations, geometric means, coefficients of variation, medians, first and third quartiles and ranges, by actual treatment and by time point. A listing including subject, week/time point (actual, planned), treatment and plasma concentrations.

Pre-dose PK samples will only be considered ‘pre-dose’ if they are collected within the 10-14 hours window post the most recent dose prior to the PK sample collection.

Population PK analysis and exposure-response analysis may be performed, with details reported separately.

## 12 Autoantibody Analyses

The presence and levels of anticentromere antibody, anti-RNA polymerase antibody, anti-topoisomerase 1 and anti-U1 small nuclear ribonucleoprotein will be evaluated and summarized descriptively for the Safety Analysis Set.

A listing of all autoantibody results will be produced.

## 14 Appendix, Schedule of Assessments (Clinical Study Protocol v2.2)

Trial Visit	Open-label Treatment Period (HZN-825 300 mg BID)										Safety Follow-up Visit   11 4 weeks after last dose of HZN-825
	1	2	3	4	5	6	7	8	9	10	
Trial Week (W)	Day 1 	W4	W10 	W16	W22 	W28	W34 	W40	W46 	W52/PD 	
Visit Window (±days)		(±3)	(±5)	(±5)	(±5)	(±5)	(±5)	(±5)	(±5)	(±5)	(±14)
Informed consent	X										
Review eligibility criteria	X										
Weight	X 					X				X	
HZN-825 dispensing	X	X	X	X	X	X	X	X	X		
Compliance		X	X	X	X	X	X	X	X	X	
mRSS 	X 			X		X		X		X	
FVC % predicted/spirometry 	X 			X		X		X		X	
MDGA	X 			X		X		X		X	
Lung HRCT	X 								X 		
DLCO 	X 					X 			X 		
Patient-reported outcome assessments											
SHAQ	X 			X		X		X		X	
PTGA	X 			X		X		X		X	
UCLA SCTC GIT 2.0	X 					X				X	
SSPRO-18	X 					X		X		X	

Trial Visit	Open-label Treatment Period (HZN-825 300 mg BID)										Safety Follow-up Visit 
	1	2	3	4	5	6	7	8	9	10	
Trial Week (W)	Day 1 	W4	W10 	W16	W22 	W28	W34 	W40	W46 	W52/PD 	
Visit Window (±days)		(±3)	(±5)	(±5)	(±5)	(±5)	(±5)	(±5)	(±5)	(±5)	(±14)
SScQoL	X 					X				X	
SF-12	X 					X				X	
Pain questionnaire	X 					X				X	
Fatigue (FACIT-F)	X 					X				X	
Raynaud's assessment 	X 				X				X		
Anchor questions											
ACR-CRISS (last week)	X 			X		X		X		X	
ACR-CRISS (overall health and change since start of trial)						X				X	
FVC (last week)	X 			X		X		X		X	
FVC (change since start of trial)						X				X	
HAQ-DI (last week)	X 			X		X		X		X	
HAQ-DI (change since start of trial)						X				X	
SSPRO-18 ( last week)	X 					X		X		X	
SSPRO-18 (change since start of trial)						X				X	

Trial Visit	Open-label Treatment Period (HZN-825 300 mg BID)										Safety Follow-up Visit 
	1	2	3	4	5	6	7	8	9	10	
Trial Week (W)	Day 1 	W4	W10 	W16	W22 	W28	W34 	W40	W46 	W52/PD 	
Visit Window (±days)		(±3)	(±5)	(±5)	(±5)	(±5)	(±5)	(±5)	(±5)	(±5)	(±14)
Pregnancy test 											
Physical examination 	X 					X				X	X
Vital signs 	X 	X	X	X	X	X	X	X	X	X	X
12-lead electrocardiogram 	X 	X		X		X				X	
Echocardiogram 	X										
Clinical laboratory safety tests 											
Chemistry	X 	X	X	X	X	X		X		X	X
Lipids	X 					X				X	
Hematology	X 	X	X	X	X	X		X		X	X
Urinalysis	X 	X	X	X	X	X		X		X	X
ESR  and hsCRP	X 									X	X
Autoantibodies 	X 									X	
PK samples 	X 	X		X		X		X			
Serum Biomarkers 											
Plasma Biomarkers 											
Adverse event assessment 	X	X	X	X	X	X	X	X	X	X	X
Prior/concomitant medications 	X 	X	X	X	X	X	X	X	X	X	X

ACR-CRISS=American College of Rheumatology-Composite Response Index in Systemic Sclerosis; BID=twice daily; DLCO=diffusing capacity of the lungs for carbon monoxide; ESR=erythrocyte sedimentation rate; FACIT-F=Functional Assessment of Chronic Illness Therapy – Fatigue Scale FVC=forced vital capacity; HAQ-DI=Health Assessment Questionnaire – Disability Index; HRCT=high resolution computed tomography; hsCRP=high-sensitivity C-reactive

protein; MDGA=Physician Global Assessment; mRSS=modified Rodnan skin score; PD=premature discontinuation; PK=pharmacokinetic; PTGA=Patient Global Assessment; QD=once daily; SARS-CoV-2=severe acute respiratory syndrome coronavirus 2; SCR=Screening; SF-12=SF-12® Health Survey; SHAQ=Scleroderma Health Assessment Questionnaire; SLCO=solute carrier organic anion transporter family member; SSc=systemic sclerosis; SScQoL=Systemic Sclerosis Quality of Life Questionnaire; UCLA SCTC GIT 2.0=University of California Los Angeles Scleroderma Clinical Trial Consortium Gastrointestinal Tract; SSPRO=scleroderma skin patient-reported outcome; VAS=visual analog scale; W=Week; WOCBP=women of childbearing potential

1. Visits may be conducted as home health visits, as available within local regions.
2. On Day 1 (Baseline), subjects will receive the first dose of HZN-825 in this extension trial in the clinic. All Day 1 assessments should be performed before the first dose of trial drug is administered in the clinic.
3. Performed as part of the Week 52 Visit of HZNP-HZN-825-301; if applicable, the result will be considered a Trial Baseline value for this extension trial.
4. Except when strictly unavoidable, the same person should perform the assessment at each evaluation during the trial. The mRSS assessment should be performed by a qualified Investigator (or designee).
5. The lung HRCT scan should be performed within  $\pm 2$  weeks of the Week 52/PD Visit.
6. DLCO can be assessed within  $\pm 2$ -weeks of the Week 28 and Week 52/PD Visits.
7. Daily electronic diaries will be completed for 4 weeks starting on Day 1, 4 weeks starting at the Week 22 Visit and 4 weeks starting at the Week 46 Visit.
8. Perform for WOCBP. Serum pregnancy test at [REDACTED] (or as needed). Urine pregnancy tests should also be done every 4 weeks after Day 1, which includes both in-clinic testing at scheduled visits prior to dosing [REDACTED] and at home (also a  $\pm 7$ -day window) by the subject and reported to the site [REDACTED]. A urine pregnancy test will also be done at the Safety Follow-up Visit.
9. A complete physical examination, including but not limited to cardiac, pulmonary, neurologic and skin assessments, as well as directed rheumatology assessments [REDACTED]
10. Vital signs (blood pressure, heart rate, respiratory rate, temperature) will be measured at each visit.
11. Additional electrocardiograms or echocardiograms will be conducted, if clinically indicated. A standard transthoracic echocardiogram will be conducted on Day 1. However, an echocardiogram that has been performed during HZNP-HZN-825-301 and within the 3 months prior to HZNP-HZN-825-302 Day 1 can serve as the Trial Baseline echocardiogram if the subject has been clinically stable.
12. See Section 9.5.3.8 for details.
13. ESR must be processed within 1 hour of the blood draw.
14. Autoantibodies include anti-centromere antibody, anti-RNA polymerase antibody, anti-topoisomerase 1 and anti-U1 small nuclear ribonucleoprotein.
15. PK samples will be collected at each of the following visits: Day 1 (pre-dose), Week 4 (pre-dose and 2 to 4 hours post-dose) and Weeks 16, 28 and 40 (pre-dose). Note: all pre-dose samples will be collected prior to any HZN-825 administration for the day.
16. Blood samples will be collected for serum and plasma biomarkers prior to dosing on [REDACTED] as well as at the [REDACTED] Visit.
17. Adverse events occurring or worsening after the first dose of HZN-825 on Day 1 through the Safety Follow-up Visit will be considered treatment-emergent adverse events for this trial. All adverse events that occur from the signing of informed consent through the Safety Follow-up Visit will be recorded. The subject should be assessed for the development of new onset of scleroderma renal crisis, new onset of left ventricular failure, new onset of pulmonary arterial

hypertension or right heart catheterization requiring treatment, gastrointestinal dysmotility requiring enteral (tube feeding) or parenteral nutrition or digital ischemia with gangrene, amputation or hospitalization requiring treatment.

18. Includes recording of herb/supplement use. See Table 9.1 for restrictions regarding medications

